**Table 13 Time Point Response Criteria (+/- non-target disease)**

| Target Lesions    | Non-Target Lesions          | New Lesions | Overall Response |
|-------------------|-----------------------------|-------------|------------------|
| CR                | CR                          | No          | CR               |
| CR                | Non-CR/Non-PD               | No          | PR               |
| CR                | Not evaluated               | No          | PR               |
| PR                | Non-PD or not all evaluated | No          | PR               |
| SD                | Non-PD or not all evaluated | No          | SD               |
| Not all evaluated | Non-PD                      | No          | NE               |
| PD                | Any                         | Yes or No   | PD               |
| Any               | PD                          | Yes or No   | PD               |
| Any               | Any                         | Yes         | PD               |

**Table 14 Time Point Response Criteria (non-target disease only)**

| Non-Target Lesions | New Lesions | Overall Response           |
|--------------------|-------------|----------------------------|
| CR                 | No          | CR                         |
| Non-CR/non-PD      | No          | Non-CR/non-PD  |
| Not all evaluated  | No          | NE                         |
| Unequivocal PD     | Yes or No   | PD                         |
| Any                | Yes         | PD                         |

 Non-CR/non-PD is preferred over SD for non-target disease since SD is used as endpoint for assessment of efficacy in trials so to assign this category when no lesions can be measured is not advised.

The best overall response is the best response recorded from the start of study treatment until patients are removed from the study for any reason (the end of treatment taking into account any requirement for confirmation). In general, the participant's best response assignment will depend on the achievement of both measurement and confirmation criteria and will be determined by combining the participant's status of target lesions, non-target lesions, and new lesions.

- **Residual Disease:** Provide the appropriate information that pertains to this study.
- **Symptomatic Deterioration:** Participants with global deterioration of health status requiring discontinuation of treatment without objective evidence of disease progression at that time, and not related to study treatment or other medical conditions should be reported as progressive disease due to "symptomatic deterioration." Every effort should be made to document objective progression even after discontinuation of treatment due to symptomatic deterioration. Symptomatic deterioration that may lead to discontinuation of treatment include, but is not limited to, symptoms such as:
  - Weight loss > 10% of body weight.
  - Worsening of disease-related symptoms (e.g., worsening dyspnea, increasing pain/increasing requirement for narcotic analgesics).
  - Decline in performance status of > 1 level on ECOG scale.

## 9.5 Confirmation Measurement

Response will be confirmed within 9 weeks.

## 9.6 Guidelines for Evaluation of Measurable Disease

All measurements should be taken and recorded in metric notation using a ruler or calipers. All baseline evaluations should be performed as closely as possible to the beginning of treatment and never more than 4 weeks before the beginning of the treatment.

The same method of assessment and the same technique should be used to characterize each identified and reported lesion at baseline and during follow-up. Imaging-based evaluation is preferred to evaluation by clinical examination unless the lesion(s) being followed cannot be imaged but are assessable by clinical exam.

- **Clinical Lesions:** Clinical lesions will only be considered measurable when they are superficial (e.g., skin nodules and palpable lymph nodes) and  $\geq 10$  mm diameter as assessed using calipers (e.g., skin nodules). In the case of skin lesions, documentation by color photography, including a ruler to estimate the size of the lesion, is recommended.
- **Chest x-ray:** Lesions on chest x-ray are acceptable as measurable lesions when they are clearly defined and surrounded by aerated lung. However, CT is preferable.
- **Conventional CT and MRI:** This guideline has defined measurability of lesions on CT scan based on the assumption that CT slice thickness is 5 mm or less. If CT scans have slice thickness greater than 5 mm, the minimum size for a measurable lesion should be twice the slice thickness. MRI is also acceptable in certain situations (e.g., for body scans).

Use of MRI remains a complex issue. MRI has excellent contrast, spatial, and temporal resolution; however, there are many image acquisition variables involved in MRI, which greatly impact image quality, lesion conspicuity, and measurement. Furthermore, the availability of MRI is variable globally. As with CT, if an MRI is performed, the technical specifications of the scanning sequences used should be optimized for the evaluation of the type and site of disease. Furthermore, as with CT, the modality used at follow-up should be the same as was used at baseline and the lesions should be measured/assessed on the same pulse sequence. It is beyond the scope of the RECIST guidelines to prescribe specific MRI pulse sequence parameters for all scanners, body parts, and diseases. Ideally, the same type of scanner should be used and the image acquisition protocol should be followed as closely as possible to prior scans. Body scans should be performed with breath-hold scanning techniques, if possible.

- **PET-CT:** At present, the low dose or attenuation correction CT portion of a combined PET-CT is not always of optimal diagnostic CT quality for use with RECIST measurements. However, if the site can document that the CT performed as part of a PET-CT is of identical diagnostic quality to a diagnostic CT (with IV and oral contrast), then the CT portion of the PET-CT can be used for RECIST measurements and can be used interchangeably with conventional CT in accurately measuring cancer lesions over time. Note, however, that the PET portion of the CT introduces additional data which may bias an investigator if it is not routinely or serially performed.

- **Ultrasound:** Ultrasound is not useful in assessment of lesion size and should not be used as a method of measurement. Ultrasound examinations cannot be reproduced in their entirety for independent review at a later date and, because they are operator dependent, it cannot be guaranteed that the same technique and measurements will be taken from one assessment to the next. If new lesions are identified by ultrasound in the course of the study, confirmation by CT or MRI is advised. If there is concern about radiation exposure at CT, MRI may be used instead of CT in selected instances.
- **Endoscopy, Laparoscopy:** The utilization of these techniques for objective tumor evaluation is not advised. However, such techniques may be useful to confirm complete pathological response when biopsies are obtained or to determine relapse in trials where recurrence following complete response (CR) or surgical resection is an endpoint.
- **Tumor Markers:** Tumor markers alone cannot be used to assess response. If markers are initially above the upper normal limit, they must normalize for a participant to be considered in complete clinical response.
- **Cytology, Histology:** These techniques can be used to differentiate between partial responses (PR) and complete responses (CR) in rare cases (e.g., residual lesions in tumor types, such as germ cell tumors, where known residual benign tumors can remain).

The cytological confirmation of the neoplastic origin of any effusion that appears or worsens during treatment when the measurable tumor has met criteria for response or stable disease is mandatory to differentiate between response or stable disease (an effusion may be a side effect of the treatment) and progressive disease.

- **FDG-PET:** While FDG-PET response assessments need additional study, it is sometimes reasonable to incorporate the use of FDG-PET scanning to complement CT scanning in assessment of progression (particularly possible 'new' disease). New lesions on the basis of FDG PET imaging can be identified according to the following algorithm:
- Negative FDG-PET at baseline, with a positive FDG-PET at follow-up is a sign of PD based on a new lesion.
- No FDG-PET at baseline and a positive FDG-PET at follow-up: If the positive FDG-PET at follow-up corresponds to a new site of disease confirmed by CT, this is PD. If the positive FDG-PET at follow-up is not confirmed as a new site of disease on CT, additional follow-up CT scans are needed to determine if there is truly progression occurring at that site (if so, the date of PD will be the date of the initial abnormal FDG-PET scan). If the positive FDG-PET at follow-up corresponds to a pre-existing site of disease on CT that is not progressing on the basis of the anatomic images, this is not PD.
- FDG-PET may be used to upgrade a response to a CR in a manner similar to a biopsy in cases where a residual radiographic abnormality is thought to represent fibrosis or scarring. The use of FDG-PET in this circumstance should be prospectively described in the protocol and supported by disease-specific medical literature for the indication. However, it must be acknowledged that both approaches may lead to false positive CR due to limitations of FDG-PET and biopsy resolution/sensitivity.

Note: A ‘positive’ FDG-PET scan lesion means one which is FDG avid with an uptake greater than twice that of the surrounding tissue on the attenuation corrected image.

## **10 SAFETY EVALUATION**

### **10.1 Adverse Events**

#### **10.1.1 Definition**

An adverse event or adverse experience (AE) is defined as any untoward medical occurrence (including an exacerbation of a pre-existing condition) associated with the use of a drug in humans, whether or not considered drug related (i.e., the event does not necessarily have to have a causal relationship with the treatment). Therefore, an AE can be ANY unfavorable and unintended sign (including an abnormal laboratory finding), symptom, or disease temporally associated with the use of a medicinal (investigational) product, whether or not considered related to the medicinal (investigational) product (attribution of ‘unrelated’, ‘unlikely’, ‘possible’, ‘probable’, or ‘definite’). In addition, each study site will also be responsible for reporting causality of AEs to Boehringer Ingelheim as per **Section 10.2.1**.

An AE is considered “unexpected” if it is not listed in the investigator brochure or is not listed at the specificity or severity that has been observed; or if an investigator brochure is not required or available, is not consistent with the risk information described in the general investigational plan in other study-related documents.

#### **10.1.1.1 Diagnosis Versus Signs and Symptoms**

If known, a diagnosis should be recorded on the CRF rather than individual signs and symptoms (e.g., record only liver failure or hepatitis rather than jaundice, asterixis, and elevated transaminases). However, if a constellation of signs and/or symptoms cannot be clinically characterized as a single diagnosis or syndrome at the time of reporting, each individual event should be recorded as an AE or SAE on the CRF. If a diagnosis is subsequently established, it should be reported as follow-up information.

#### **10.1.1.2 Adverse Events Occurring Secondary to Other Events**

In general, AEs occurring secondary to other events (e.g., cascade events or clinical sequelae) should be identified by their primary cause. For example, if severe diarrhea is known to have resulted in dehydration, it is sufficient to record only diarrhea as an AE or SAE on the CRF.

However, clinically significant AEs occurring secondary to an initiating event that are separated in time should be recorded as independent events on the CRF. For example, if a severe gastrointestinal hemorrhage leads to renal failure, both events should be recorded separately on the CRF.

#### **10.1.1.3 Abnormal Laboratory Values**

Only clinically significant laboratory abnormalities that require active management will be recorded as AEs or SAEs on the CRF (e.g., abnormalities that require study drug dose

modification, discontinuation of study treatment, more frequent follow-up assessments, further diagnostic investigation, etc.).

If the clinically significant laboratory abnormality is a sign of a disease or syndrome (e.g., alkaline phosphatase and bilirubin 5 x the upper limit of normal associated with cholecystitis), only the diagnosis (e.g., cholecystitis) needs to be recorded on the Adverse Event CRF.

If the clinically significant laboratory abnormality is not a sign of a disease or syndrome, the abnormality itself should be recorded as an AE or SAE on the CRF. If the laboratory abnormality can be characterized by a precise clinical term, the clinical term should be recorded as the AE or SAE. For example, an elevated serum potassium level of 7 mEq/L should be recorded as “hyperkalemia”

Observations of the same clinically significant laboratory abnormality from visit to visit should not be repeatedly recorded as AEs or SAEs on the CRF, unless their severity, seriousness, or etiology changes.

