### **3.2.2 Secondary Objectives**

- To assess median progression free survival. This will be assessed via the Response Evaluation Criteria in Solid Tumors (RECIST) version 1.1 guidelines after every 3 cycles (9 weeks) of therapy].
- To assess median overall survival from the date of enrollment to the time of death will be documented.
- To assess the objective response rate as measured by RECIST v 1.1.
- To assess the toxicity of dose regimen using the CTEP NCI Common Terminology Criteria for Adverse Events (CTCAE Version 4.0).

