### **Endpoints**

- **Phase I**
  - Primary: Establishment of the recommended phase II dose.
- **Phase II**
  - Primary: The primary endpoint is the progression free survival (PFS) at 18 weeks. This will be assessed via the Response Evaluation Criteria in Solid Tumors (RECIST) version 1.1 guidelines after every 3 cycles (9 weeks) of therapy.
  - Secondary: Median progression free survival will be established. Median overall survival from the date of enrollment to the time of death will be documented. Aggregate rates of adverse events as measured by CTCAE v 4.0 will be recorded to objectively measure toxicities of the two agents.

The primary objectives of this study are:

- Phase I: To estimate the maximum tolerated dose (MTD) and examine the dose-limiting toxicities of nintedanib when administered with capecitabine within the study population and, establish the Recommended Phase II Dose (RP2D).
- Phase II: To assess progression free survival at 18 weeks. This will be assessed via the Response Evaluation Criteria in Solid Tumors (RECIST) version 1.1 guidelines after every 3 cycles (9 weeks) of therapy.

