study or at last visit before being lost to follow-up. The survival time is defined as the time from treatment until the survival event or censoring. The PFS will be as defined in the primary analysis. The OS and PFS are considered bivariate time-to-event data, and will be summarized using standard Kaplan-Meier methods. Estimates of median OS and PFS will be obtained with corresponding 90% confidence intervals. If the true median OS or PFS with the new treatment is 10.2 or 3.0 months, a 60% improvement over historical controls (6.4 and 1.9 month median OS and PFS, respectively); then Phase II estimates of the median will have interval widths of approximately 9.9 or 3.2 months for OS and PFS, respectively. The observed toxicities and adverse events will be reported as frequencies and relative frequencies, with toxicity rates estimated by 90% Wilson confidence intervals. If the true overall toxicity or adverse event rate is 0.10 to 0.50; then Phase II estimates of these rates will have interval widths of approximately 0.17 to 0.26.

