### **12.4.1 Adverse Event**

The frequency of toxicities will be tabulated by grade across all dose levels and cycles. The frequency of toxicities will also be tabulated for the dose estimated to be the MTD. All participants who receive any study treatment will be considered evaluable for toxicity.

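### Low-grade laboratory toxicity would be understated: abnormalities reach the AE page only if they need active management, and no toxicity table is graded from the laboratory values

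*Combined protocol and SAP*

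**What the plan says.** **Recording.** Section 10.1.1.3 limits what is entered: "Only clinically significant laboratory abnormalities that require active management will be recorded as AEs or SAEs on the CRF". Its examples of active management are broad: a dose change, stopping treatment, closer follow-up or further investigation. Section 10.1.1.1 also lets a diagnosis replace the laboratory sign: "record only liver failure or hepatitis rather than jaundice, asterixis, and elevated transaminases".

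**Definition and reporting grid.** Section 10.1.1 is wider: "an AE can be ANY unfavorable and unintended sign (including an abnormal laboratory finding), symptom, or disease temporally associated". Tables 15 and 16 in Section 10.2.2 call for grade 1 and 2 events to be reported, whatever the attribution in Phase I, and when at least possibly related in Phase II.

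**Analysis.** Toxicity is a secondary objective (Section 3.2.2). The endpoint in Section 12 reads: "Aggregate rates of adverse events as measured by CTCAE v 4.0 will be recorded to objectively measure toxicities of the two agents". Section 12.4.1 adds: "The frequency of toxicities will be tabulated by grade across all dose levels and cycles". Section 12.3 reports frequencies, "with toxicity rates estimated by 90% Wilson confidence intervals". None of these names the data source or asks for a worst-grade or shift table from laboratory values. Section 12.5 mentions changes in laboratory values, but as part of ongoing safety monitoring.

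**Measurement.** Blood counts and chemistry are scheduled on Day 1 of every cycle, on Day 8 of cycles 1 and 2 in Phase I, and at End of Treatment (Sections 8.3, 8.5 and 8.7).

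**The concern.** A CTCAE rate for a laboratory parameter should depend on the measured value. Under Section 10.1.1.3 it depends on whether someone had to act on that value. Two patients with the same ALT could be counted differently, and two sites could differ in what they regard as needing management.

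The Wilson interval does not help. It expresses sampling error in the recorded proportion and takes ascertainment as complete. If part of the low-grade events never reaches the AE page, the interval is centred too low and its stated confidence no longer applies to the true rate.

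This matters most for liver enzymes. Section 1.4 names them as the leading dose-limiting toxicity in early trials and a frequent finding in later ones. A stated secondary objective would rest on incomplete counts even though the samples are drawn on schedule.

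**Working it through.** **Step 1. Which abnormalities trigger action?**

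- *AST/ALT above 5x ULN:* interruption (Table 4), dose adjustment (Table 9), AESI when bilirubin is not raised (Section 10.2), and DLT if drug-related in cycle 1 (Section 6.4). Captured.
- *AST/ALT raised together with bilirubin above 1.5x ULN:* interruption and adjustment from 3x ULN (Tables 4 and 9); AESI and DLT from 2.5x ULN (Sections 10.2 and 6.4). Captured.
- *Bilirubin above ULN, platelets at or below 100,000, or ANC at or below 1000 at cycle start:* the next cycle cannot begin (Section 6.3). Captured.
- *Isolated AST/ALT up to 5x ULN with normal bilirubin:* no interruption in Table 4, no adjustment in Table 9, no block on the next cycle in Section 6.3. Section 6.4 labels values above 2.5x ULN as grade 2 and above 5x ULN as grade 3, so this range includes grade 2. Table 10 holds drug for grade 2 events, but it covers other AEs, and liver enzymes are handled separately in Section 6.5.3. Can go unrecorded.
- *Mild count or chemistry changes that delay nothing:* can go unrecorded.

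**Step 2. Reproduce the plan's interval widths.** Section 12.3 gives widths of about 0.17 to 0.26 for true rates of 0.10 to 0.50. With n = 36 and z = 1.645, the Wilson width is

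2z·√[p(1−p)/n + z²/(4n²)] / (1 + z²/n).

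Here z²/n = 2.706/36 = 0.0752 and z²/(4n²) = 2.706/5184 = 0.00052.

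- p = 0.10: 2 × 1.645 × √(0.00250 + 0.00052) / 1.0752 = 0.168.
- p = 0.50: 2 × 1.645 × √(0.00694 + 0.00052) / 1.0752 = 0.264.

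Both match. They contain no allowance for under-recording.

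**Step 3. Effect of under-recording.** The documents do not give the recorded share s, so it is varied. Each patient with a true event is assumed to be recorded independently with probability s, so the recorded count is binomial with n = 36 and rate s × R, where R is the true rate. Coverage is the probability that the 90% Wilson interval contains R. Two values of R are used: 13.7%, the ALT figure in Section 1.6.2, and 30%, an assumption.

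| Recorded share s | R = 13.7%: expected rate (patients) | Coverage | R = 30%: expected rate (patients) | Coverage |
|---|---|---|---|---|
| 100% | 13.7% (4.9) | 92% | 30% (10.8) | 90% |
| 75% | 10.3% (3.7) | 89% | 22.5% (8.1) | 73% |
| 50% | 6.9% (2.5) | 72% | 15% (5.4) | 29% |
| 25% | 3.4% (1.2) | 35% | 7.5% (2.7) | 2% |

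Check of the 72%: the interval for 1/36 is 0.6–11.5% and misses 13.7%; for 2/36 it is 1.9–15.5% and includes it. At the upper end, 9/36 has a lower limit of 15.2% and misses, but counts that high are very unlikely here. At rate 0.0685, P(0) = 0.9315³⁶ = 0.078 and P(1) = 36 × 0.0685 × 0.9315³⁵ = 0.206, so coverage is about 1 − 0.078 − 0.206 = 0.716. At rate 0.03425 the same two terms are 0.285 and 0.364, giving 0.351.

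**The case against.** **The action rules catch much more than Table 4 alone suggests.** This stands. Active management is defined broadly, and Step 1 shows that marked liver elevations, raised bilirubin at cycle start and cycle-delaying cytopenias all meet it. If Table 10 is applied to laboratory findings, many non-liver grade 2 events do too. A reader might infer that laboratory toxicity as a whole is understated, or that dose finding is compromised. The documents do not support that: the loss falls on low grades.

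**Laboratory findings are not the drug's predominant adverse events.** This stands. Sections 1.4 and 1.6.1 put gastrointestinal events and fatigue first; liver enzymes lead only among dose-limiting toxicities.

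**The data source is not stated, and Section 10.1.1 with Tables 15 and 16 would admit low-grade laboratory findings.** This stands in part. The AE page as source is an inference, but the natural one: the Section 12 endpoint and the Synopsis both speak of adverse event rates. The wider definition does not remove the problem, because Section 10.1.1.3 is the specific rule for laboratory values and contradicts it.

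**The 13.7% is not a true laboratory rate.** This stands. It is a reported drug-related AE rate from a lung cancer trial whose recording rule is not given. It serves only as an illustrative value of R. A reader might also infer that the results could not be compared with other nintedanib trials; nothing in the documents shows how those trials recorded laboratory events.

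**The values may not be in the database.** This stands. The tests are scheduled, but no section says that all numeric results enter the eCRF. GGT, listed in Section 1.6.1 among the dose-limiting enzyme elevations, is not on the chemistry panel.

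**Conclusion.** The concern holds for low-grade laboratory toxicity. Followed as written, the plan would report rates of laboratory abnormalities that needed management, presented as CTCAE toxicity rates. The gap is mainly isolated AST/ALT up to 5x ULN with normal bilirubin, plus mild count and chemistry changes. Section 10.1.1.3 also conflicts with Section 10.1.1 and Tables 15 and 16, and that needs resolving whatever the size of the bias.

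The direction of the bias is clear if the AE page is the source; its size is not known. It could be slight (89% coverage at a true 13.7% with three quarters recorded) or large (29% at an assumed true 30% with half recorded). These figures rest on an assumed recorded share and an assumed true rate. It would go too far to say that the reported interval must exclude the truth: with 2 of 36 recorded it still includes 13.7%.

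DLT assessment and the RP2D are largely protected. The primary endpoint, its alpha and power, and the sample size are unaffected. This is a reporting weakness in a secondary objective, worth correcting because the remedy is cheap.

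**What to change.** In Section 12.4.1, derive laboratory toxicity from the numeric blood count and chemistry values at all on-study time points: Day 1 of each cycle, Phase I Day 8, End of Treatment and unscheduled tests.

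- For each parameter with CTCAE v4.0 grades, report per patient the worst post-baseline grade that exceeds the baseline grade, and put the 90% Wilson interval on that rate. Counting only worsening matters because Section 5.1 admits patients with liver metastases and AST/ALT up to 2.5x ULN, and Section 10.1.1.4 does not count unchanged baseline conditions as AEs.
- Add a shift table from baseline grade to worst grade.
- Report the AE-page counts beside these, labelled as laboratory abnormalities requiring management.
- Confirm that the numeric values are entered in the eCRF.
- Reconcile Section 10.1.1.3 with Section 10.1.1 and Tables 15 and 16.

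No extra visits or blood draws are needed. The costs are some data entry if it is not already planned, a few more tables, and higher reported laboratory toxicity rates that are not limited to drug-related events. GGT cannot be graded from the scheduled panel, and Phase II has no scheduled mid-cycle tests, so short-lived changes between visits would still be missed.
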